### **6.11.3. Prohibited Medications and Non-Drug Therapies**

#### **6.11.3.1. Related to the Study**

- Any conventional DMARDs other than MTX (including hydroxychloroquine, leflunomide, sulphasalazine, minocycline, ciclosporin, azathioprine).
- Any biologic agent (such as TNF inhibitors such as adalimumab, etanercept, infliximab, certolizumab pegol, golimumab or non-TNF inhibitors (including abatacept, rituximab, tocilizumab and belimumab) and any anti-rheumatic investigational compounds.
- IA corticosteroids are strongly discouraged within 8 weeks prior to Day 1, and then through Week 52.
  - However, IA corticosteroids may be used in a limited fashion as treatment for severe RA flares.
  - No more than 1 joint per 24-week period or 2 joints per 52-week period should be injected.
  - No single injection should exceed 40 mg of triamcinolone (or equivalent) and the total dose of IA corticosteroid should not exceed 80 mg of triamcinolone (or equivalent) during the 52-week period.
- IV and/or IM steroids are not permitted for at least 28 days prior to Day 1, or throughout the study.
- Live vaccines should not be administered for 12 weeks after the last dose of GSK3196165. Furthermore, GSK3196165 and MTX are immunosuppressive and may therefore reduce immunological response to concurrent vaccination. In addition, investigators are expected to assess vaccination status, including against influenza and pneumococcus according to local guidelines.

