### 9.3.2. Analysis Data Sets

For the binary endpoints (e.g. proportion of subjects achieving remission at 24 weeks), subjects with missing efficacy data (caused by prematurely discontinued subjects or otherwise) or subjects who received rescue treatment will be imputed as non-responders. A dataset will be created with this imputation and will be referred to as Non-Responder Imputation (NRI) and will be the primary dataset used for all binary endpoints.

In addition to the Non-Responder Imputation dataset for binary endpoints, for all efficacy endpoints a Observed Case (OC) dataset will be created, whereby the data are as collected or observed in the study and no imputation is made for missing data. All continuous endpoints will be analysed using the OC dataset and all data will be listed using the (OC) dataset.

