#### 4.4.2 Protocol Deviations

Protocol deviations (PDs) will be managed and reported according to PAREXEL Standard Operating Procedures (SOPs).

Details will be given in the Protocol Deviation Specification (PDS) document, which will include detailed information regarding definitions, classifications, tracking and management of PDs.

PDs will be categorised as major or minor as further described in the PDS.

PDs will also be classified into the following categories: Informed Consent, Inclusion/Exclusion Criteria, Withdrawal Criteria, IP Admin/Study Treat, Disallowed Medications, AE/SAE, Visit Schedule, Procedures/Tests, Other.

Observable PDs that can only be identified by project team members during the monitoring, but cannot be programmed, will be tracked and reconciled with programmable (data driven) PDs, that can be programmed from the recorded data.

A combined PD dataset will include all PDs.

Special considerations are needed for (potentially) unblinding PDs, which will be handled in separate unblinded areas with restricted access.

Summaries of the number and percentage of subjects with a major/minor protocol deviation will be provided by randomised treatment group and by type of deviation (Analysis population: Randomised Population).

A by-subject listing of all protocol deviations will be provided.

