## 4.5.2 Missing Data for Efficacy and Safety Endpoints

### 4.5.2.1 Missing Data for Efficacy Endpoints

Missing visit data for each efficacy endpoint will be handled as described in Sections 3.2 and 4.3.1. For each continuous endpoint, change from baseline will be missing at visits with missing post-baseline values or where data were imputed to missing.

For the binary endpoints, subjects with missing efficacy data, early withdrawals, subjects who exceed the allowed dose of corticosteroid, who received new parenteral corticosteroids or more than one intra-articular corticosteroid injection within a 24 week period, or subjects who received rescue treatment will be imputed as non-responders and therefore treated as a failure (e.g. no DAS28(CRP) remission or no moderate/good EULAR response).

For subjects who exceed the allowed dose of corticosteroid, who received new parenteral corticosteroids or more than one intra-articular corticosteroid injection within 24 weeks or subjects who received rescue treatment, continuous efficacy endpoints will be set to missing.

- Missing efficacy data: visits with missing data (due to a missed visit or missing component of a composite endpoint) should be set to treatment failure.
- Early withdrawals (including subjects that are withdrawn at Week 36 due to lack of EULAR response): only visits following the early withdrawal visit should be set to treatment failure.
- Prednisone equivalent >10 mg/day: the visit after a period (time from previous visit up to the day before the current visit) of average daily corticosteroid use exceeding 10 mg/day prednisone and all following visits should be set to treatment failure (continuous endpoints will be set to missing).
- Parenteral corticosteroids: all visits after a subject received any new parenteral corticosteroids (e.g. intravenous and intra-muscular) should be set to treatment failure (continuous endpoints will be set to missing).
- Intra-articular corticosteroids: all visits after the second intra-articular corticosteroid injection within a 24 week period should be set to treatment failure (continuous endpoints will be set to missing).
- Rescue: subjects who rescue to 180 mg dose at Week 14 or 26 should be set to treatment failure at that visit and all subsequent visits (continuous endpoints will be set to missing).

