### Methotrexate

Numbers and percentages of subjects who increased or decreased their MTX dose or missed a MTX dose during the conduct of the study will be shown separately for administrations before escalation and after escalation.

A by-subject by-period listing of treatment compliance ratio for GSK3196165 will be provided.

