#### **4.13.1 Primary Analysis**

The sample size for the primary analysis and hence the overall sample size for the study is based on detecting a 30% difference from placebo in the proportion of subjects in remission (DAS28 score <2.6) at Week 24 of the 52 week double-blind treatment period for each GSK3196165 dose.

Using a Fisher's exact test, a sample size of 35 subjects per arm will provide approximately 90% power to detect a difference of 30% in the proportion of subjects in remission between each GSK3196165 dose (33%) and placebo (3%) at the two-sided  $\alpha=0.05$  level at 24 weeks. The placebo rate of 3% is based on a literature review of current therapies presenting DAS28(CRP) remission results. No adjustments will be made to the sample size to account for the multiple doses in this Phase 2 study.

The least significant difference this sample size will detect is an approximate 17% difference from placebo.

The sample size will not be increased to account for dropouts and all dropouts within the treatment period will be classed as non-remitters for the primary analysis.

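### The Week 24 failure rule does not cover a subject who adds a prohibited RA drug, or exceeds the permitted MTX dose, and stays in the study

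*SAP*

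**What the plan says.** Protocol 9.3.2 states the principle for binary endpoints: besides subjects with missing data, "subjects who received rescue treatment will be imputed as non-responders". It does not define rescue treatment. SAP 4.3.1 repeats the term, adds corticosteroid criteria, and sends the reader to 4.5.2 for the rule in each case.

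SAP 4.5.2.1 then gives six operative bullets: missing data; early withdrawal (only visits after the withdrawal visit fail); average oral prednisone equivalent above 10 mg/day; any new parenteral corticosteroid; a second intra-articular injection within 24 weeks; and rescue, worded as "subjects who rescue to 180 mg dose at Week 14 or 26 should be set to treatment failure at that visit and all subsequent visits". The same visits are set to missing for continuous endpoints.

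Other RA drugs are dealt with elsewhere, but not as efficacy failures:

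- Protocol 6.11.3.1 prohibits "Any conventional DMARDs other than MTX (including hydroxychloroquine, leflunomide, sulphasalazine, minocycline, ciclosporin, azathioprine"), and also biologics and investigational anti-rheumatic compounds.
- Protocol 6.1 permits an MTX increase only after a reduction, and only back to the dose before it.
- Protocol 5.4 does not list use of a prohibited RA drug as a reason for withdrawal.
- SAP 4.4.2 has a deviation category "Disallowed Medications", which is summarised and listed. SAP 4.7 summarises RA medication by arm.
- SAP 4.8 reports "Numbers and percentages of subjects who increased or decreased their MTX dose or missed a MTX dose during the conduct of the study" without separating a permitted return from a larger increase.
- SAP 4.3 analyses every endpoint in the ITT population by randomised group. There is no per-protocol set and no sensitivity analysis on this point.

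**The concern.** The corticosteroid bullets show that the SAP means to stop other RA treatment from being credited to the randomised arm. As written, however, a second joint injection within 24 weeks makes a subject a failure, and an added biologic does not. If a subject adds such a drug, stays in the study and reaches remission, the primary endpoint credits that remission to the randomised arm. The continuous endpoints share the gap, because they blank only the visits that the binary rule fails.

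Few remitters are expected, especially on placebo, so each wrongly classified subject carries weight. Without a rule set in advance, any decision about such a subject would be made after the primary data were known.

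**Working it through.** **1. Who falls through.** Take a subject who starts another RA drug before Week 24.

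- Stops study drug and has an early-withdrawal visit before the Week 24 window: later visits fail. Covered.
- Oral prednisone raised above 10 mg/day: the corticosteroid bullet applies. Covered, even though Protocol 6.11.1.1.1 keeps the subject on visits.
- No Week 24 DAS28(CRP): missing-data bullet. Covered.
- Adds the drug, stays in the study, observed DAS28(CRP) below 2.6 at Week 24: no bullet applies. Counted as a remitter.
- Stops study drug, and the early-withdrawal visit maps to Week 24: only visits after it fail, so its value counts. Under SAP 4.5.3 a withdrawal visit more than 7 days after a target day goes to the next visit. Week 22 is Day 155 and Week 24 is Day 169, so the window is Day 155+8=163 to Day 169+7=176.

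Escalation at Week 26 comes after the endpoint, so only the Week 14 part of the rescue bullet affects Week 24 remission.

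**2. Reproducing the plan's figure.** SAP 4.13.1 says that "a sample size of 35 subjects per arm will provide approximately 90% power to detect a difference of 30% in the proportion" in remission, for 33% on active and 3% on placebo, by Fisher's exact test at two-sided 0.05. Enumerating both binomials with n=35 and rejecting when p≤0.05 gives 90.9%. All nine cells of SAP Table 11 reproduce within 1 point. The stated least significant difference of 17% is 6/35 v 0/35 (6/35=17.1%, p=0.025).

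**3. What one subject does.** One subject is 1/35=2.9 points.

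- One active remitter reclassified as a failure: 6/35 v 0/35 (p=0.025) becomes 5/35 v 0/35 (p=0.054); 8/35 v 1/35 (p=0.028) becomes 7/35 v 1/35 (p=0.055).
- One extra placebo subject counted as a remitter: 8/35 v 1/35 (p=0.028) becomes 8/35 v 2/35 (p=0.084).

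**4. What k such subjects do on average.** Assume that k subjects in one arm are counted as remitters only because of the other drug, so that arm's rate becomes 0.03+k/35. The middle column compares a raised placebo rate with 33% on active. The last column assumes no true effect (3% v 3%) and raises only the active arm.

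| k | Power, k on placebo | Chance of p≤0.05, k on active, no true effect |
|---|---|---|
| 0 | 90.9% | 0.04% |
| 1 | 78.6% | 0.6% |
| 2 | 63.5% | 3.1% |
| 3 | 48.3% | 9.3% |

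**5. Plausible size.** The documents give no frequency, so these are assumed ranges.

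- If 1% to 3% of 210 subjects are affected, that is 2.1 to 6.3 in all, or 0.35 to 1.05 per arm of 35. If 33% of those are in remission, it is about 0.1 to 0.35 per arm.
- If 3% to 10% of placebo subjects take another RA drug and 33% to 50% of them remit because of it, the placebo rate is 0.03+0.03×0.33=4.0% up to 0.03+0.10×0.50=8.0%. Power is then 87% down to 67%.

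**The case against.** The strongest reply is that the main route to another RA drug is already closed. Protocol 6.11.2 sets a change of therapy after an excessive flare against staying on study treatment, Protocol 4.6.3 lets the investigator withdraw a subject at any time, and stopping study drug triggers an early-withdrawal visit, after which visits fail. This stands, and it confines the point to the two groups in step 1.

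The second reply is that rescue treatment in Protocol 9.3.2 and SAP 4.3.1 already includes outside drugs, because the heading of Protocol 6.11.2 names DMARD and biologic rescue medications. That reading is possible. But the text under the heading describes only escalation and a possible change of therapy, SAP 4.3.1 defers to 4.5.2, and the bullet there names only 180 mg. A programmer following it would not fail these subjects.

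Third, use would be visible in the deviation, RA-medication and MTX summaries. That is true, but it does not change the primary result.

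Two stronger readings are tempting. A reader might infer that any subject given another RA drug counts as a remitter; the missing-data and early-withdrawal bullets show otherwise. A reader might also infer that the 180 mg arm gains most, because it has no dose escape. The documents give no use by arm. Their own Week 12 assumptions (change of -1.0 on placebo, -2.32 on 180 mg) would make flares no less likely on placebo or low doses. Week 12 responders who flare later have no dose escape before Week 24 in any arm.

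**Conclusion.** The gap is real and limited, and it should be fixed. It concerns subjects who add a prohibited RA drug, or exceed the MTX dose that Protocol 6.1 permits, and stay in the study with an observed Week 24 remission, plus those whose early-withdrawal visit maps to Week 24. The MTX part is the weaker: nothing in the documents equates an out-of-protocol increase with starting a biologic.

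The direction depends on the arm: use on placebo dilutes the effect, and use on an active dose inflates it. Under the assumed 1% to 3%, about one subject per arm or fewer is affected, and not all would remit. The p-value pairs sit at the 0.05 boundary by choice; they show that one subject can matter, not that one will. All p-values and power figures use Fisher's test, as the sample-size section does. The primary analysis is a logistic GEE model adjusted for baseline DAS28(CRP), so they are indicative only.

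**What to change.** Before unblinding, add one rule to SAP 4.5.2.1 and mirror it in 4.3.1. It applies from the first use after Day 1 of a conventional DMARD other than MTX, a biologic or an investigational anti-rheumatic agent prohibited by Protocol 6.11.3.1, or of an MTX dose above that permitted by Protocol 6.1. Visits after that use are treatment failure for binary endpoints, including an early-withdrawal visit after such use, and missing for continuous endpoints. State that a permitted return to the MTX dose before a reduction does not count as failure.

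This extends the approach that the SAP already applies to corticosteroids. It needs SAP wording and programming only: concomitant medication is recorded throughout, and MTX dates and weekly doses are in the eCRF (Protocol 6.8). The downside is that a few remitters may be lost, including some who would have remitted without the added drug.

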## 4.2. Treatment Arms and Duration

In the “dose selection” component of the study, subjects will be randomised (1:1:1:1:1) to placebo or one of five subcutaneous GSK3196165 doses, in combination with MTX (at a dose between 15-25 mg previously received for at least 12 weeks, with a stable and tolerated dose and route of administration for  $\geq 4$  weeks).

Treatment with GSK3196165 will be given as a single subcutaneous (SC) injection by an unblinded administrator (shielded to subjects) weekly for 5 injections (Days 1, 8, 15, 22, 29), then EOW thereafter beginning at Day 43 (Week 6).

GSK3196165/placebo must be administered on the same day each week  $\pm 1$  day for the first 5 weekly doses. Following this GSK3196165/placebo must be administered on the same day EOW  $\pm 3$  days.

After the Day 85 (Week 12) administration:

- “Escape therapy” is provided for all subjects not on the 180 mg dose:
  - Subjects in the placebo, 22.5 mg, 45 mg, 90 mg and 135 mg arms will be escalated in a double-blind fashion to the 180 mg (or the highest remaining) dose at Week 14 if they have failed to achieve EULAR good/moderate response\* at Week 12.

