Once the effective therapeutic dose(s) have been selected at the interim analyses, treatment allocation could be adapted so that randomisation is stopped to the ineffective doses and future subjects are randomised to only the effective dose(s) and placebo. Subjects already in the study will remain on the arm to which they were randomised. There is a rescue option for all subjects, whereby the subjects can be escalated to the highest remaining dose for the remainder of the study. The randomisation ratio will be 1:1:1:1:1:1 across the original 6 arms of the study (*i.e.*, n=35 in each dosing group). However, due to the re-allocation of subjects once the effective dose(s) are known, it is likely that at the end of the study there will be more subjects in the effective dose groups and placebo.

Medical monitoring will happen in the form of monthly blinded data review meetings which include but are not limited to:

- Medical review of protocol deviations
- Medical review of high panic lab alerts
- Cumulative data review (includes summaries of reason for screening failures, disposition, adverse events, serious adverse events, disease related events and chest x-rays)
- Medical review of coding

Further information on the medical monitoring can be found in the Medical Data Review Plan (MDRP) and the Medical Monitoring Plan (MMP).

The primary analysis will occur 24 weeks after the last subject was randomised. The final analysis will occur after the end of the study which is defined as the last subject's last visit.

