#### 4.3.1 Analysis Datasets

For each of the efficacy evaluations of binary endpoints, subjects with missing efficacy data, early withdrawals, subjects who received more than 10 mg/day of prednisone equivalent oral corticosteroids, subjects with any new use of parenteral corticosteroids, more than one intra-articular corticosteroid injection within a 24 week period, or subjects who received rescue treatment will be imputed as non-responders and therefore treated as a failure (e.g. no DAS28(CRP) remission or no moderate/good EULAR response). Imputation rules for each case are described in section 4.5.2:

A dataset will be created with these imputation rules and will be referred to as the NRI dataset. The NRI dataset will be the primary dataset used for all binary efficacy endpoints. Imputed response for each binary endpoint will be presented by visit and subject in listings.

For the efficacy evaluations of continuous endpoints, results recorded for subjects who received rescue treatment or exceeded 10 mg/day prednisone equivalent oral corticosteroids, subjects with any new use of parenteral corticosteroids, more than one intra-articular corticosteroid injection within a 24 week period, or subjects who received rescue treatment will be set to missing at the same visits that were set to non-responder for the binary endpoints. This is a change from protocol section 9.3.2. A dataset will be created and will be referred to as the Set-to-Missing (STM) dataset.

For safety endpoints, no imputation for missing data will be done.

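### After Week 14, rescue counts as failure in every arm except 180 mg, which cannot be rescued, so non-responder-imputed binary endpoints are not comparable between 180 mg and the other arms

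*SAP*

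**What the plan says.** Protocol 4.2 and SAP 3.1.3 describe escape therapy that "is provided for all subjects not on the 180 mg dose". In the other five arms, a subject without a good or moderate EULAR response at Week 12 escalates at Week 14. A subject still on the randomised dose with DAS28(CRP) above 3.2 at Week 24 escalates at Week 26.

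For binary endpoints, SAP 4.5.2.1 states that "subjects who rescue to 180 mg dose at Week 14 or 26 should be set to treatment failure" at that visit and all later ones. For continuous endpoints, SAP 4.3.1 states that results "will be set to missing at the same visits that were set to non-responder for the binary endpoints".

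The Week 36 EULAR rule, with withdrawal at Week 38, covers every arm. SAP 4.3.1 makes the non-responder imputation (NRI) dataset primary for all binary efficacy endpoints. No planned analysis applies the escape criteria to the 180 mg arm. Multiple imputation is optional, ad hoc, limited to DAS28(CRP) and assumes data missing at random.

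**The concern.** Counting rescue as failure is a fair between-arm measure only if rescue can occur in every arm. Take two subjects with the same DAS28(CRP) history, both above 3.2 at Week 24. The one on 135 mg is a non-responder from Week 26 whatever happens next. The one on 180 mg is judged on observed values.

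Remission, EULAR response and ACR response at all assessment timepoints are major secondary endpoints in a study meant to inform Phase 3 dose selection. Sustained remission and Major Clinical Response are built on the same NRI data and must include Week 52. A rescued subject in another arm cannot reach either through a run that begins after rescue; a 180 mg subject with the same Week 24 score can. Displays by dose could therefore show a step at 180 mg that comes from the rule and not from the drug.

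**Working it through.** **Step 1, the plan's own figure.** SAP 4.13.1 states: "Using a Fisher's exact test, a sample size of 35 subjects per arm will provide approximately 90% power" for remission of 33% against 3%, two-sided 0.05. Power is the sum, over all outcomes (x, y) with Fisher p ≤ 0.05, of Bin(x; 35, 0.03) × Bin(y; 35, 0.33). This gives 90.9%. All nine cells of SAP Table 11 reproduce within 1 point. The stated 17% least significant difference is 0/35 against 6/35 (6/35 = 17.1%, p = 0.025).

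**Step 2, simulation inputs.**
- From the documents: SD of DAS28(CRP) change 1.0; Week 12 mean change -2.24 (the 135 mg assumption); 33% remission at Week 24; the EULAR table; both escape rules; the Week 36 withdrawal rule in both arms.
- Assumed, because not given: baseline DAS28 mean 5.3 to 5.8 with SD 0.9; correlation of change between visits 0.4 to 0.8; mean change flat after Week 24.

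Both arms have the same true DAS28(CRP) distribution, with 1,000,000 simulated subjects per scenario. One arm follows the 180 mg rules. In the other, response at a visit is (criterion met) and (not rescued earlier).

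**Step 3, binary endpoints.** Entries are 180 mg against the equally effective other dose, in percent, with the gap in points.

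| Baseline mean / correlation | 5.8 / 0.4 | 5.8 / 0.6 | 5.8 / 0.8 | 5.3 / 0.6 |
|---|---|---|---|---|
| Rescued Week 14; Week 26 | 8.9; 42.4 | 9.0; 41.6 | 9.0; 41.2 | 7.1; 43.2 |
| Remission, Week 24 | 33.0 v 32.2 (0.8) | 33.0 v 32.6 (0.4) | 33.0 v 32.9 (0.1) | 33.0 v 32.7 (0.3) |
| EULAR, Week 24 | 95.5 v 88.0 (7.5) | 95.6 v 88.8 (6.8) | 95.5 v 89.8 (5.7) | 91.3 v 87.1 (4.2) |
| EULAR, Week 28 | 95.6 v 48.1 (47.5) | 95.6 v 49.2 (46.4) | 95.5 v 49.8 (45.7) | 91.3 v 48.7 (42.6) |
| Remission, Week 52 | 32.8 v 26.3 (6.5) | 32.8 v 28.7 (4.1) | 33.0 v 31.2 (1.8) | 32.6 v 28.4 (4.2) |
| EULAR, Week 52 | 92.0 v 47.5 (44.5) | 92.6 v 49.0 (43.6) | 93.3 v 49.7 (43.6) | 86.0 v 47.9 (38.1) |

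If the mean change instead keeps improving after Week 24 (-2.4 at Week 24, -2.6 at Week 52), the gaps are roughly 36 to 50 points for EULAR response over Weeks 28 to 52 and 3 to 9 points for Week 52 remission.

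With a weaker Week 12 mean of -1.54, the Week 24 remission gap is 0.9 to 2.4 points. In an extreme slow-onset case (-1.0 at Week 12, yet 33% remission at Week 24) it is 8.2 points.

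The same comparison can be read against placebo. Take the plan's placebo change of -1.0 at Week 12, an assumed 10% Week 24 remission, baseline mean 5.8 and correlation 0.6, and give 180 mg no effect at all. EULAR response is then 73.0% v 49.7% at Week 24 (23.3 points) and 73.2% v 17.0% at Week 28 (56.2 points).

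**Step 4, continuous endpoints.** In the four tabulated scenarios the observed mean change in the rescued arm looks better than in the 180 mg arm, because poor responders leave it:
- Week 24: by 0.07 to 0.14 DAS28 units (for example -2.59 for 180 mg against -2.69).
- Week 28: by 0.24 to 0.46 units (for example -2.59 against -2.94).

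A missing-at-random estimate, regressing on baseline and earlier changes, stands in for the planned MMRM. It returns -2.614 at Week 24 against a true -2.614, both on the scale before the score's lower limit is applied. Rescue depends on DAS28(CRP) values that the model uses, so this is expected.

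**Step 5, the symmetric rule.** If everyone meeting an escape criterion is a non-responder, equal doses show equal rates by construction. At baseline 5.8 and correlation 0.6, Week 24 remission is 32.6% in both. Power against 3% is 90.0% at 32.5%, against 90.9% at 33%.

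**The case against.** The best defence is that Protocol 9.3.2 defines failure by receipt of rescue treatment. A 180 mg subject receives none, so later values are real observations on the randomised dose. In the tabulated cases about half the arm meets a criterion (for example 9.0% + 41.6% = 50.6%). A symmetric rule would relabel many true moderate responders as failures, which is a choice of estimand. This stands, and it is why the symmetric version should accompany the current analysis and not replace it.

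It is also true that SAP 4.4.1 tabulates escalations by arm and SAP 4.9.2.2 plans subject-level DAS28 plots. These show how many were rescued, but they do not correct the response rates.

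Three stronger readings are tempting, and the documents do not support them:
- *That the set-to-missing endpoints also favour 180 mg.* Step 4 shows the opposite for observed means and about neutrality for MMRM on DAS28(CRP).
- *That the primary result is compromised.* Week 26 rescue falls after the Week 24 assessment. Only a Week 12 EULAR non-responder who is in remission at Week 24 is affected.
- *That dose selection rests on the distorted rates.* The named dose-response endpoint and the arm-dropping criterion in SAP Table 4 use Week 12 change. Protocol 10.8.1 links the Week 24 analyses to later development. No direct test of 180 mg against another active dose is planned. The asymmetry enters through unequal contrasts with placebo and through reading rates across doses.

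**Conclusion.** The concern holds for binary NRI endpoints after Week 14. Between equally effective doses the rule favours 180 mg by about 4 to 8 points for Week 24 EULAR response, 36 to 50 points for EULAR response from Week 28 to Week 52, and 2 to 9 points for Week 52 remission. Week 24 remission shifts by about 1 point or less unless response is weak at Week 12. The Week 12 dose-response is unaffected.

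The sizes depend on the assumed baseline, correlations and later means. The direction was the same in every scenario. ACR response, sustained remission and Major Clinical Response follow the same rule but were not simulated. For continuous endpoints other than DAS28(CRP), rescue depends on a score outside their model; any remaining bias there was not computed. The Week 24 dose-response model, planned without covariates, leans towards the rescued arms if fitted to raw set-to-missing values.

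**What to change.** 1. In SAP 4.5.2.1 and 4.9.2.2, pre-specify for all binary endpoints after Week 14 a between-arm analysis in which every subject meeting the Week 12 or Week 24 escape criterion, 180 mg included, is a non-responder from Week 14 or Week 26. Show it beside the current NRI analysis, use it whenever 180 mg is compared with the other arms, and record it in SAP 4.14.
2. Leave the observed 180 mg continuous data in place. Base continuous comparisons after Week 14, including the Week 24 dose-response, on MMRM estimates and not on raw set-to-missing means.
3. Reconcile two wordings. Protocol 4.3 and SAP 3.1.4 describe rescue as open to all subjects, while Protocol 4.2 and SAP 3.1.3 exclude the 180 mg arm. SAP 4.5.2.1 names only 180 mg as the rescue dose, while SAP 3.1.3 also allows the highest remaining dose.

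The cost is one derived flag, extra tables and lower 180 mg response rates in the symmetric version. No new data are needed and treatment does not change.
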